6.4 Other Efficacy Analyses

Clinical Efficacy Variables

Binary secondary endpoints described in Section 4.3.2 will be analyzed as exploratory endpoints at Week 32 using count and percentages on each of the four different treatment regimens. Point estimate and 95% CI using normal approximation will be provided as well. The data occurred after initiation of the rescue medication will be imputed using NRI for the subsequent visits in this summary.

Continuous secondary endpoints described in Section 4.3.2 will be analyzed as exploratory endpoints at Week 32 by summary statistics (number of subjects, mean, 95% confidence interval, standard deviation, median, minimum, maximum) for each treatment regimen. All observed data will be used to summarize the continuous exploratory endpoints. The data occurring after initiation of the rescue medication will be overwritten by the last observation prior to treatment rescue (Last observation carried forward: LOCF) for the subsequent visits in this summary.

Ultrasound Variables

For ultrasound assessment at Week 16, analysis will be performed using similar methods to those described for the secondary continuous efficacy endpoints. In addition, baseline weight will also be included as an additional covariate in MMRM. The LS mean, 95% CI and standard error for each randomized treatment group and the LS mean of the treatment difference, its associated 95% CI and p-values will be presented.

For the ultrasound assessment at Week 32, summary statistics (number of subjects, mean, 95% confidence interval, standard deviation, median, minimum, maximum) will be presented for each treatment regimen. All observed data will be used to summarize the

continuous exploratory endpoints. The data occurring after initiation of the rescue medication will be overwritten by LOCF for the subsequent visits in this summary.

Summary of Efficacy Endpoints by Visit

Summary of the primary and secondary efficacy endpoints at the scheduled time points will be presented by two treatment groups in the Part 1 analysis and by four treatment regimens in the long-term analysis. Achievement of each MDA component as binary endpoints will be summarized similarly as well.

For Part 1 analysis, binary efficacy endpoints will be analyzed in a similar way as the primary endpoint and continuous efficacy endpoints will be analyzed from the same MMRM model for the Wk16 endpoints.

For the long term by-visit summary of binary and continuous efficacy endpoints, summary statistics will be provided by the four treatment regimens and by visit. For binary endpoints, subjects who were rescued after Week 24 will be considered as non-responders for all subsequent visits after initiation of the rescue medication in this summary. For continuous efficacy endpoints, the Data occurred after initiation of the rescue medication will be overwritten by LOCF for the subsequent visits in this summary.

6.5 Efficacy Subgroup Analyses

The primary efficacy endpoint will be examined in the subgroups listed in [Table 1](#) below. Point estimate of the treatment differences and 95% CI between the randomized treatment groups will be presented for each subgroup. No p-value will be provided for subgroup analysis. If any of the resulting subgroups for a variable has fewer than 20% of the planned study size (i.e., < 48 subjects), the subgroup analyses for that variable will not be presented.

Table 1. Subgroups for Efficacy Analysis

Subgroup Factor	Categories
Age	< 40, [40, 65), ≥ 65
Sex	Male or Female
BMI	< 25 kg/m ² or ≥ 25 kg/m ²
Race	White, Non-white
Geographic region	US, Western Europe/Canada, Eastern Europe/Middle East/Africa, Latin America, Japan/Asia/Pacific
Prior MTX usage	≤ 3 months or > 3 months

6.6 Efficacy Analysis for Rescued Patients

For the subjects who take at least of one dose of rescue medication, MDA status will be evaluated after rescue at the Week 28 and Week 32. Point estimate and 95% CI using normal approximation will be provided for the response rate of the MDA by 4 treatment regimens as well as overall. The subjects who are rescued at Week 24 and Week 28 will be summarized separately.

7.0 Safety Analyses

7.1 General Considerations

There will be 2 sets of safety analyses to be performed.

1. Safety analyses during Part 1 (up to Week 16).
2. Safety analyses during Part 2 (Week 16 to Week 32).

Safety analyses will include reporting of adverse events (AEs), laboratory, and vital signs measurements. Treatment-emergent AEs will be summarized and reported. Missing safety data will not be imputed. Part 1 and Part 2 safety analyses will be carried out using the Safety Population Part 1 and Safety Population Part 2, respectively.

Safety Analysis during Part 1 (up to Week 16)

Standard safety analysis by the "as treated" treatment groups of ADA 40 mg eow + MTX 15 mg ew and MTX 20 - 25 mg or highest tolerable dose ew will be performed on safety data up to Week 16. No protocol-defined treatment switching will occur prior to this time point.

Frequency tables of subjects with treatment-emergent adverse events (TEAEs) by system organ class (SOC) and by preferred term (PT) as in the Medical Dictionary for Regulatory Activities (MedDRA) dictionary will be provided by as-treated treatment groups.

Observed values in all continuous laboratory parameters and vital signs variables at each visit will be summarized by "as treated" treatment groups. Frequency tables of subjects meeting criteria for potentially clinically significant vital sign values and for potentially clinically significant laboratory values will be provided by as-treated treatment groups. Missing safety data will not be imputed.

Safety Analysis during Part 2 (Week 16 to Week 32)

Similar standard safety analysis by the "as treated" treatment groups will be performed on safety data from Week 16 to Week 32 based on Safety Population Part 2.

7.2 Analysis of Adverse Events

7.2.1 Treatment-Emergent Adverse Events

Treatment-emergent adverse events (TEAEs) will be defined based on the following:

- Part 1: TEAEs will be defined as any event with an onset date that is on or after the first dose of Part 1 study drug, and
 - no more than 70 days after the last dose of ADA and 30 days after the last dose of MTX, if the subject discontinued prematurely from Treatment Part 1 or did not enter the Part 2, or
 - prior to date of first dose of Part 2 study drug if the subject entered Part 2.

- Part 2: TEAEs will be defined as any event with an onset date that is on or after the first dose of Part 2 study drug and with an onset date no more than 70 days after the last dose of ADA or 30 days after the last dose of MTX.

Events where the onset date is the same as the study drug start date are assumed to be treatment-emergent, unless the study drug start time and the adverse event start time are collected and the adverse event start time is prior to the study drug start time. If an incomplete onset date was collected for an adverse event, the event will be assumed to be treatment emergent unless there is other evidence that confirms the event was not treatment-emergent (e.g., the event end date was prior to the study drug start date).

Adverse event data will be presented by SOCs and PTs using MedDRA Version 21.1 or most up to date version.

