Treatment-emergent AEs are defined as AEs that begin either on or after the first dose of the study medication, and up to within 70 days after the last dose of the study medication. All treatment emergent AEs will be coded using the Medical Dictionary for Drug Regulatory Activities (MedDRA[®]). The number and percent of subjects experiencing AEs will be tabulated by system organ class and preferred term. In addition, a summary of AEs by severity and relationship to study drug will be presented. AEs, which are serious, severe, or life-threatening, which lead to premature study discontinuation will be listed and described in detail. Adverse events of special interest (AESI) will also be tabulated.

Statistical Methods (Continued):

Safety:

Observed values of vital signs and laboratory variables at each visit will be summarized for all treated subjects, and change from baseline in selected lab variables will be compared between treatment groups using a one way ANOVA. The last evaluation prior to the first dose of study drug will be used as Baseline for the analyses in Part 1. For selected parameters, a listing of all subjects with any laboratory determination meeting Common Toxicity Criteria (CTC) (Version 3) of Grade 3 or higher will be provided. Shift tables for changes from Baseline according to the normal range will also be provided for laboratory variables.

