5.1.2.2 Part 2 (Open-Label Treatment Period)

After completing the randomized-open label treatment period at Week 16, subjects will be assigned to Arms 1-4 of Part 2 (as described in Section 5.1), based on the achievement of MDA and initial randomized treatment, and treated for additional 16 weeks. Starting at Week 24, there will be rescue treatment option based on not achieving MDA and investigator's judgment. During this study period, subjects will visit the study site monthly through Week 32. A \pm 2-day window is permitted around scheduled study visits. Subjects will be dispensed study drugs at the Week 16 Visit for administration during the visit or at the regularly scheduled day for MTX.

No study drug will be administered or injected after the final visit (Week 32 Visit). Subjects may discontinue study drug treatment at any time during study participation. Subjects who end study participation early will have a Premature Discontinuation (PD) Visit and complete the procedures outlined for the PD Visit in Appendix C as soon as possible after the last dose of study drug and preferably prior to the administration of any new therapies.

Follow-Up Period

Subjects may discontinue their study participation at any time. Subjects that end study participation early will have a PD Visit. All subjects will have a follow-up phone call 70 days (\pm a 7 day window) after the last administration of adalimumab to obtain information on any new or ongoing AEs. For subjects taking only MTX, the follow-up phone call will occur 70 days (\pm 7 day window) after the last administration of MTX.

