5.5.1.2 Methotrexate

MTX will be administered open-label either orally as tablets or subcutaneously by pre-filled pens (sc) as outlined below.

- Subjects randomized to Arm 1/Part 1 will continue at the stable dose of MTX 15 mg ew (as described in Section 5.1 and Table 3).
- Subjects randomized to Arm 2/Part 1 will increase MTX dose to 20-25 mg or highest tolerable dose ew as described below (see also Section 5.1 and Table 3).

- Subjects assigned to Arm 1/Part 2 will discontinue MTX at Week 16 (Section 5.1 and Table 3). MTX should be discontinued immediately and completely at the Week 16 Visit (subjects will not taper-off MTX).
- Subjects assigned to Arm 2/Part 2 will continue at the stable dose of MTX 15 mg ew after the Week 16 visit (see also Section 5.1 and Table 3).
- Subjects assigned to Arm 3/Part 2 will continue MTX at 20-25 mg or highest tolerable dose ew after the Week 16 Visit (as described in Section 5.1 and Table 3).
- Subjects assigned to Arm 4/Part 2 will continue MTX at 20-25 mg or highest tolerable dose ew after the Week 16 Visit (as described in Section 5.1 and Table 3).
- Subjects entering the rescue arm at or after Week 24 will have MTX introduced or escalated at the Investigator's discretion. For the recommended rescue treatment regimens see Section 5.1 Overall Study Design and Plan: Description.

During the study subjects should remain on their regular MTX administration schedule as prior to the study and MTX should be taken on the same day and approximately the same time of day ew.

The escalation of MTX dose in Arm 2/Part 1 should be in the increments of 5 mg every two weeks until the MTX dose of 20-25 mg ew is reached.^{27,66,67} The dose escalation begins on Day 1, starting with MTX 20 mg ew as the first MTX dose at or after Day 1, as applicable according to the MTX administration schedule prior to study enrolment. The dose of MTX should only be escalated providing there are no clinical and/or laboratory signs of MTX intolerance or toxicity.

In the case of clinical and/or laboratory signs of MTX intolerance/toxicity, MTX dose may be de-escalated by 5 mg, including during the MTX escalation period.^{67,68} The subject may stay on the highest tolerable MTX dose which is lower than 20-25 mg ew if MTX intolerance/toxicity occurred, see Section 6.1.7 for additional information. MTX dose should not exceed 25 mg ew in this study.

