6.1.4 Adverse Event Collection Period

All adverse events reported from the time of study drug administration until 70 days following discontinuation of study drug administration have elapsed will be collected, whether solicited or spontaneously reported by the subject. In addition, serious adverse events and protocol-related nonserious adverse events will be collected from the time the subject signed the study-specific informed consent. Adverse event information will be collected and recorded on the appropriate eCRFs.

Subjects will be contacted 70 days (\pm 7 day window) following study drug discontinuation for an assessment of any new or ongoing AEs. All SAEs and all ongoing adverse events reported during the 70-day follow-up phone call must be captured in the clinical database.

Adverse event information will be collected as shown in [Figure 2](#).

Figure 2. Adverse Event Collection

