8.1.5 Statistical Analyses of Safety

Safety analyses will be carried out using safety population, which includes all subjects that received at least one dose of study medication. Treatment-emergent AEs will be summarized and reported.

Treatment-emergent AEs are defined as AEs that begin either on or after the first dose of the study medication, and up to within 70 days after the last dose of the study medication. All treatment emergent AEs will be coded using the Medical Dictionary for Drug Regulatory Activities (MedDRA[®]). The number and percent of subjects experiencing AEs will be tabulated by system organ class and preferred term. In addition, a summary of AEs by severity and relationship to study drug will be presented. AEs, which are serious, severe, or life-threatening, which lead to premature study discontinuation will be listed and described in detail. Adverse event of special interest (AESI) will also be tabulated.

Observed values of vital signs and laboratory variables at each visit will be summarized for all treated subjects, and change from baseline in selected lab variables will be compared between treatment groups using a one way ANOVA. The last evaluation prior

to the first dose of study drug will be used as Baseline for the analyses in Part 1. For selected parameters, a listing of all subjects with any laboratory determination meeting Common Toxicity Criteria (CTC) (Version 3) of Grade 3 or higher will be provided. Shift tables for changes from Baseline according to the normal range will also be provided for laboratory variable.

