5.0 Analysis Populations and Important Subgroups

5.1 Analysis Populations

Intent-to-Treat Population Part 1

The Intent-To-Treat Part 1 (ITT Part 1) population comprises all subjects who were randomized and received at least one dose of the study medication during the Part 1 period. The data collected up to Week 16 will be included and analyzed by the treatment

group assignment given at the time of randomization, even if the subject does not receive the correct treatment, is not compliant to the protocol procedures, or does not follow the protocol until completion.

Intent-to-Treat Population Long Term

The Intent-To-Treat Long Term (ITT LT) population comprises all subjects who entered Part 2 period and received at least one dose of Part 2 study medication. The data collected from randomization and up to Week 32 will be included and analyzed by the four treatment regimens as follows:

- ADA 40 mg eow + MTX 15 mg ew/ADA 40 mg eow
- ADA 40 mg eow + MTX 15 mg ew/ADA 40 mg ew + MTX 15 mg ew
- MTX 20 - 25 mg or highest tolerable dose ew
- MTX 20 - 25 mg or highest tolerable dose ew/ADA 40 mg eow + MTX 20 - 25 mg or highest tolerable dose ew

Per Protocol Population

In order to evaluate the impact of major protocol violations on the results of the trial, additional analysis of the primary effectiveness variable may be conducted on the per protocol population, which consists of all ITT Part 1 subjects who entered the randomized period of the study and did not meet any major protocol violation during the Part 1 of the study. The determination of major protocol violation will be finalized prior to the final database lock.

Safety Population Part 1

The Safety population Part 1 consists of all subjects who received at least one dose of the study medication during the Part 1 period. The data collected up to Week 16 will be included and analyzed by the two "As treated" treatment groups in Part 1. "As treated" is determined by the treatment a subject received during majority of the subject's drug exposure time in the analysis period, regardless of the treatment randomized.

Safety Population Part 2

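### SAP 7.2.1 counts TEAEs for only 30 days after the last MTX dose where the protocol counts 70, and leaves the limit unclear for subjects on both drugs

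*SAP*

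**What the plan says.** The protocol has one window for all study medication. Section 8.1.5 counts events from the first dose "up to within 70 days after the last dose of the study medication", and the synopsis agrees: "and up to within 70 days after the last dose of the study medication". Section 5.1 states that ADA and MTX are both supplied as study drugs, so the 70 days covers MTX. Data collection matches. Section 6.1.4 says that adverse events "until 70 days following discontinuation of study drug administration have elapsed will be collected", and section 5.1.2.2 says: "For subjects taking only MTX, the follow-up phone call will occur 70 days".

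SAP 7.2.1 sets limits by drug:

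- **Part 1**, for subjects who stop early or do not enter Part 2: "no more than 70 days after the last dose of ADA and 30 days after the last dose of MTX". For everyone else, Part 1 counting ends at the first Part 2 dose.
- **Part 2**: "with an onset date no more than 70 days after the last dose of ADA or 30 days after the last dose of MTX".

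The SAP gives no reason for the 30 days, does not flag it as a departure from the protocol, and has no rule for a subject who took both drugs. SAP 3.0 says that the SAP is based on protocol Amendment 3 and elaborates its methods.

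**The concern.** There are two defects.

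First, two current texts define the same safety outcome differently. A team following the SAP will report TEAE counts that do not meet the protocol's definition, and will leave out of the tables events that the protocol requires sites to collect. The definition in 7.2.1 also feeds the overview, severity and relationship tables.

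Second, the SAP rule cannot be programmed unambiguously for subjects on both drugs. *And* can mean that an event must satisfy both limits, or simply that each drug has its own limit. *Or* points to the later limit. Two programmers could produce different counts from the same data. If each drug keeps its own limit, or the later limit governs, early leavers in the two randomised Part 1 arms are counted over windows of different length, so the safety comparison is no longer like for like.

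**Working it through.** The plan computes no figure here. Both windows are definitions, so the check is day arithmetic.

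**Subjects whose only study drug is MTX.** These are Arm 2/Part 1 subjects who leave early or do not enter Part 2, and unrescued Arm 3/Part 2 subjects. The protocol counts to last dose + 70 and the SAP to last dose + 30. Days dropped: 70 − 30 = 40, and 40/70 = 57%. If the follow-up call comes at the early edge of its ±7-day window, on day 63, 63 − 30 = 33 of the 63 days covered are dropped.

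**Subjects on both drugs.** Let A and M be the days of the last ADA and MTX doses.

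- Both limits must hold: min(A + 70, M + 30)
- Per-drug or later limit: max(A + 70, M + 30)
- Protocol: max(A, M) + 70

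Days counted after the later of the two last doses:

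| Last doses | Both limits | Later limit | Protocol |
|---|---|---|---|
| Same day | 30 | 70 | 70 |
| ADA 13 days before MTX | 30 | 57 | 70 |
| MTX 6 days before ADA | 24 | 70 | 70 |
| ADA 56 days before MTX | 14 | 30 | 70 |

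For example, a subject who stops both drugs on day 56 is counted to day 86 or to day 126. On the later-limit reading, an early leaver with same-day last doses has a 70-day window in the ADA + MTX arm, against 30 days in the MTX arm.

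**Illustrative size of the MTX-only shortfall against the protocol.** The documents give no AE rate. Assume that a proportion p of subjects has at least one AE over 112 days (p = 0.3, 0.5, 0.7), with constant hazard that continues off drug and equal ascertainment throughout. The probability of no AE by day t is then S(t) = (1 − p)^(t/112).

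- *Part 1.* Assume 10% dropout, with the stopping day s uniform on 0 to 112. The shortfall is 0.1 × mean[S(s + 30) − S(s + 70)] = 0.91, 1.31 and 1.47 points for the three values of p. In an arm of 120 that is 0.0091 × 120 = 1.1 to 0.0147 × 120 = 1.8 subjects.
- *Part 2, days counted from Week 16.* Assume the last MTX dose at Week 31, day 105. Counting ends on day 105 + 30 = 135 under the SAP and day 105 + 70 = 175 under the protocol. S(135) − S(175) = 7.8, 9.5 and 8.2 points. The planned 20% MDA rate in 120 subjects gives 24 in Arm 3, so the shortfall is 24 × 0.078 = 1.9 to 24 × 0.095 = 2.3 subjects, before dropout and rescue.

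**The case against.** **The SAP may refine the protocol, and drug-specific limits are a natural refinement.** This is fair as far as it goes. A plain drug-by-drug reading, 70 days for ADA and 30 for MTX, fits both bullets. A reader might infer that the two parts deliberately follow opposite rules, or that counting stops 30 days after MTX in every arm. The text establishes neither: the 30-day stop is certain only where MTX is the sole study drug. But the drug-by-drug reading still departs from the protocol without explanation, and the SAP does not say that it is the one intended.

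**Arm 1/Part 2.** In this arm "MTX should be discontinued immediately and completely at the Week 16 Visit" while ADA continues, so a reader might infer that TEAE counting ends about a month into Part 2. The documents do not support that. The Part 2 bullet says *or*, so the ADA limit remains available. With last MTX on day 105 and last ADA on day 210 (assumed days), max(210 + 70, 105 + 30) = 280, the same as the protocol's 210 + 70 = 280. Nothing is lost.

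**The period wording may make the point moot.** For Part 1, SAP 5.1 says: "The data collected up to Week 16 will be included and analyzed by the two". Sections 5.1 and 7.1 bound Part 2 similarly at Week 32. This may only label the periods. If it truncates AE counting, the 30-day limit removes nothing further from Part 2 completers, because Week 32 comes before day 135. The wording would then conflict with the post-dose windows in 7.2.1, so it needs a clarifying sentence in any case.

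**Little is at stake.** This largely stands. SAP 7.2.2 lists SAEs, deaths and AEs leading to discontinuation, and the Amendment 3 rationale places post-treatment AEs in the AE listing. What changes is which events enter the tables; no data are lost.

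**Conclusion.** The point holds and should be fixed. For MTX-only subjects the SAP leaves 40 of the protocol's 70 post-dose days out of the TEAE tables; this follows from the text with no assumption. For subjects on both drugs the limit is undefined, with a window anywhere from 30 to 70 days when the last doses coincide. On a per-drug or later-limit reading the randomised arms have unequal windows.

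The effect is limited. Part 1 is touched only through subjects who leave early or do not enter Part 2, and Part 2 is descriptive and non-randomised. The primary endpoint is unaffected. The illustrative shortfalls, about 0.9 to 1.5 points in Part 1 and 7.8 to 9.5 points in Part 2, depend on the assumed AE rate, dropout and last-dose days. They apply to MTX-only subjects compared with the protocol and should not be read as differences between arms.

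**What to change.** In SAP 7.2.1, use one rule for both parts and all arms: onset on or after the first dose of that part's study drug, and no more than 70 days after the last dose of any study drug, ADA or MTX, whichever is later. This is the definition in protocol 8.1.5. Keep the existing cuts at the first Part 2 dose and at the start of rescue. Add one sentence that this window governs the AE tables where the Week 16 and Week 32 period wording in SAP 5.1 and 7.1 might suggest otherwise.

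The cost is SAP wording and slightly higher TEAE counts, mainly in MTX-only subjects. One limit should be acknowledged. For subjects who received ADA, protocol 5.1.2.2 times the follow-up call from the last ADA dose, so the call may fall slightly under 70 days after the last MTX dose. With last ADA at Week 30 and last MTX at Week 31, it falls 70 − 7 = 63 days after MTX, or 63 − 7 = 56 at the early edge of the call window.
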